8.2.1 Analysis of Fluid Dynamics/Change

Bioimpedance measurement

It is hypothesized that changes in the intracellular and extracellular fluid ratios as measured by multifrequency bioimpedance will yield the most relevant pilot data indicative of treatment success. At present there is no indication of the magnitude of the effect expected using bioimpedance. However, since this is a comparative study, any difference in ECF/ICF change will be evaluated between the three groups. This will be determined using a linear mixed model with repeated measures.

For the within day measures the change in ECF/ICF will be calculated, and used as the dependent variable. Assigned group and day of visit will be forced into the model to allow for comparisons between groups and changes over time ECF/ICF ratio at baseline, BMI, time of day measurements are taken, activity level (number of hours upright and ambulatory), age, number of hours utilizing compression garment, will be tested for inclusion in the model.

To evaluate the between day outcome the change in ECF/ICF from baseline (pre-treatment) will be calculated for each follow up visit (post-treatment), with assigned group and day of visit forced into the model. Identical confounding variables will be used as for the within day analysis.

Final analysis will examine the change in ECF/ICF ratio from baseline to end of final treatment using the same model as above.

Local Tissue Water

Local Tissue Water (LTW) will be assessed prior to and post-treatment at each visit as for the bioimpedance data. The analysis will therefore be undertaken in a similar way to the bioimpedance data.

Perometry

Perometry will be used to estimate limb volume pre and post treatment. The analysis will therefore be undertaken in an identical way as for the bioimpedance measurements.

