5.2 Endpoints

The endpoints for this study include:

- Intra/extracellular fluid changes (bioimpedance)
- Limb fluid volume changes (whole and segmental) (perometry and bioimpedance)
- Superficial tissue characteristics (induration/depth and thickness of fascia) using ultrasound and tonometry.
- Tissue water assessment utilizing Moisture Meter D and Ultrasound
- Symptom assessment (MyMOP)
- Qualitative interviews
- Activity level between and post treatment (pedometer and patient log)

5.3 Safety Endpoints: Safety endpoints will include incidence and severity of complications. A clinician will assess any signs and symptoms of acute infection, DVT, cellulitis, pain or any other need for medical intervention and the possible need for a subject to discontinue the study.

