7.4.3 Bioelectrical Impedance: A Bioimpedance Spectroscopy (BIS) device will also be used to quantify changes in intra- and extra-cellular fluid at each visit. BIS utilizes the characteristics of frequency dependent current flow to detect fluid changes. Measurements are generated by a low frequency electrical signal transmitted to the patient from the device through skin surface electrodes. The measurement is imperceptible to the subject and is not confounded by weight or muscle changes that may occur in the limbs. Appendix B contains the study procedure for bioimpedance.

7.4.4 Limb Volume Measurement: Limb volume measures will be taken at each visit for both legs of the subject. The site will conduct limb volume measurements using an optoelectronic system (Pero-System, Perometer, Appendix C). The perometer utilizes infra red light beams to measure limb volume more rapidly than the circumferential tape measure method. These systems have been validated against circumferential measures to a correlation coefficient of .977 in leg subjects.¹⁷ The perometer can be used for whole leg or segmental (upper/lower) measurements. Perometer measurement will be taken twice on each leg and the average used.

7.4.5 Tonometry: Tissue assessment/fibrosis will be evaluated with use of a tonometer at anatomically defined locations on the affected leg and on the trunk. The Tonometer is a mechanical device that gives

an indication of the resistance of tissue to compression. It is used in lymphoedema to give an estimate of the extent of pitting and fibrotic induration. Tonometry readings of the affected areas will be compared to readings taken pre-treatment intervention. Appendix D contains the Tonometer operating instructions and the body points for this trial.

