8.2 Efficacy Analysis

Analysis will be undertaken for the following groups:

Group A: One lower extremity treatment per day using program L1 with the pressure set to “normal” utilizing the full garment set over 12 days. Total number of treatment hours=12.

Group B: Two lower extremity treatments per day (am and pm) using program L1 with pressure set to “normal” utilizing the full garment set over 5 days. Total number of treatment hours=10.

Group C: Two consecutive treatments 2 times a day (am and pm) using program L1 with pressure set to “normal” utilizing the full garment set over 5 days. Total number of treatment hours=20.

This study is planned to have a maximum of 30 completed subjects, 10 in each group with unilateral or bilateral primary or secondary leg lymphoedema. Each subject will receive the FT as per the groups described above. This small sample size will not offer a powered statistical analysis for any single outcome measurement, but is designed to estimate treatment effects for each proposed endpoint for evaluation in a subsequent clinical trial. This study is designed to determine both which measurement endpoints are most sensitive to the variable dosing protocols and to determine which endpoint should be defined as the primary end-point in a larger investigation of compression “dosage”. The study will be used to find the effect size for comparisons between the doses and from this to estimate a suitable sample size for a definitive study.

Subjects with missing data for the study outcomes will be included in the intention to treat analysis. However, the study will continue to enroll until there are 10 subjects in each arm that complete all study visits. After 30 patients have been randomised, those patients who fail to complete all treatment visits will be replaced until all data are available for 10 subjects in each study group. Data from the subjects who fail to complete will be used to determine the adherence to therapy in each randomised group.

Study analysis will be conducted for “within day” change as well as “between day” change. “Within day” change is defined as a comparison of pre-treatment measures against post-treatment measures following the last treatment of the day. “Between day” change is defined as a comparison of pre-treatment outcomes on treatment day 1 compared to post-treatment outcome measures on the final treatment day (day 12 for group A, day 5 for groups B and C).

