This study will evaluate FT-induced changes in three types of outcome measurements categorized as:

- (a) fluid dynamics (measured via bioimpedance; moisture meter; and perometry);
- (b) subcutaneous tissue density (a presumed surrogate marker of tissue fibrosis measured via tonometry)
- (c) patient reported outcomes addressing symptoms, treatment satisfaction; and treatment adherence (measured via MYMOP; patient survey and adherence diary).

Although this is a pilot study with multiple outcomes, the outcome measurement order as listed above indicates a *pre hoc* identification of the order of significance of the outcome measures (change in fluid dynamics > change in tissue fibrosis > change in patient outcomes) in this short-term dose-finding trial.

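### Bioimpedance is analysed only as the ECF/ICF ratio, so the pilot has no planned effect estimate for ECF, ICF or bioimpedance-derived limb fluid volume

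*Combined protocol and SAP*

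**What the plan says.** Section 5.2 lists two endpoints that use bioimpedance: "Intra/extracellular fluid changes (bioimpedance" and "Limb fluid volume changes (whole and segmental) (perometry and bioimpedance". Section 7.4.3 says the spectroscopy device "will also be used to quantify changes in intra- and extra-cellular fluid at each visit".

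Section 8.2 describes an unpowered pilot with 10 completers per arm. It is meant to give an effect estimate for every endpoint put forward, and to show "which measurement endpoints are most sensitive to the variable dosing protocols", so that a primary endpoint and sample size can be chosen for a definitive trial. It ranks the outcome categories in advance: "change in fluid dynamics > change in tissue fibrosis > change in patient outcomes".

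Within the first category, section 8.2.1 expects that "changes in the intracellular and extracellular fluid ratios as measured by multifrequency bioimpedance will yield the most relevant pilot data". The three-group comparison and the within-day, between-day and final bioimpedance analyses all take change in ECF/ICF as the outcome. Baseline ECF/ICF is among the covariates to be tested for inclusion. Limb volume is modelled from perometry only. Local tissue water and perometry get analyses like the bioimpedance one.

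**The concern.** The plan measures two compartments and a volume by bioimpedance, then carries forward one derived number. A ratio discards information in two ways: proportional changes in its parts cancel, and a change in it does not show which part moved.

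In a confirmatory trial with a justified ratio endpoint this could be a settled choice. Here the choice of metric is itself a study output. If ECF or bioimpedance volume responds to dose more clearly than the ratio, the planned analysis will not show it, and the definitive trial could be sized on the less sensitive metric. Section 8.2.1 also says the size of the expected bioimpedance effect is unknown, so the documents offer no evidence for fixing on the ratio in advance.

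**Working it through.** The plan gives no effect size, SD or power for bioimpedance, so there is no design figure to reproduce. The check has two parts.

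**1. Tracing each quantity to its analysis**

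| Quantity | Where named | Analysis in 8.2.1 |
|---|---|---|
| ECF/ICF ratio | 8.2.1 | within-day, between-day, final |
| ECF, ICF separately | 7.4.3 (5.2 is ambiguous) | none |
| Limb fluid volume, bioimpedance | 5.2 | none |
| Limb volume, perometry | 5.2, 7.4.4 | same models as the ratio |
| Local tissue water | 5.2 | similar models |

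**2. What the ratio can and cannot show** (all volumes and percentages are assumed, for illustration)

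Cancellation: (k × ECF)/(k × ICF) = ECF/ICF for any k. With ECF down 5%:
- ICF unchanged: 0.95/1 = 0.95, ratio down 5%.
- ICF down 2.5%: 0.95/0.975 = 0.974, ratio down 2.6%.
- ICF down 5%: 0.95/0.95 = 1, ratio unchanged.

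In litres, start from ECF 4.0 and ICF 5.0, ratio 0.800:
- Both down 10%: 3.6/4.5 = 0.800. No change, with 0.40 + 0.50 = 0.90 L lost.
- ECF down 5%, ICF down 10%: 3.8/4.5 = 0.844. The ratio rises 5.6% with 0.20 + 0.50 = 0.70 L lost.

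Attribution, from the same start:
- ECF falls 5%: 3.8/5.0 = 0.76, with 0.20 L lost.
- ICF rises to 5.0/0.95 = 5.26: 4.0/5.26 = 0.76, with 0.26 L gained.

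The two ratio changes are identical.

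Precision: let log ECF and log ICF changes have equal SD s and correlation r (both assumed). Then Var(log ratio) = s² + s² − 2rs² = 2(1 − r)s². Relative to log ECF this is 2.0 at r = 0, 1.0 at r = 0.5 and 0.4 at r = 0.8.

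Signal and noise together: if log ICF moves by a fraction f of the log ECF change, the standardised effect on the log ratio, relative to that on log ECF, is (1 − f)/√[2(1 − r)].

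| | r = 0 | r = 0.5 | r = 0.8 |
|---|---|---|---|
| f = 0 | 1/1.414 = 0.71 | 1/1 = 1.00 | 1/0.632 = 1.58 |
| f = 0.5 | 0.5/1.414 = 0.35 | 0.5/1 = 0.50 | 0.5/0.632 = 0.79 |
| f = 1 | 0 | 0 | 0 |

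Above 1 the ratio is the more sensitive metric; below 1, ECF is. The documents give neither f nor r. The collected data would estimate both.

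**The case against.** The case for leaving the plan alone has real substance.

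- **Endpoint wording.** A reader might infer that section 5.2 sets an ECF-alone endpoint that goes unanalysed. It does not name one. The slash form there can be read as the relation between compartments, which 8.2.1 then analyses. Section 7.4.3 describes what the device measures and does not define an endpoint. This stands, but the gap for bioimpedance volume does not depend on that reading.
- **Failure scenario.** A reader might infer that any regimen removing fluid from both compartments would look ineffective. That holds only for equal proportional falls. Nothing in the documents says ICF falls with treatment, and section 3.1 frames one therapy goal around interstitial, hence extracellular, fluid. If mainly ECF falls, the ratio responds.
- **Backstop.** Perometry and local tissue water sit in the same top-ranked category and get comparable models, so a proportional loss could show there. There is no formal primary endpoint, so a flat ratio would not decide the trial. This stands in part: neither measure separates the compartments or supplies the bioimpedance half of the volume endpoint.
- **Quality of the ratio.** A reader might infer that the ratio is the noisier or inferior metric. The table above shows it can be better or worse.
- **Baseline scaling.** A 5% ECF fall is 0.05 × 0.8 = 0.04 at a ratio of 0.8 and 0.05 × 1.6 = 0.08 at 1.6 (assumed), against ln(0.95) = −0.051 for both on the log scale. But baseline ECF/ICF is already a candidate covariate, arms are randomised, and 8.2.1 does not say whether change is absolute or relative. This is no separate fault, although a tested covariate may not be retained.
- **Multiplicity.** More candidates ranked on 10 subjects per arm makes the apparent winner look better than it is. This stands and is taken up in the fix.

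**Conclusion.** The concern holds in a limited form. Section 8.2.1 reduces bioimpedance to one ratio and gives no effect estimate for ECF, ICF or bioimpedance-derived limb fluid volume. That falls short of what section 8.2 says the pilot is for. The volume omission follows directly from setting 5.2 beside 8.2.1. The compartment omission rests on 7.4.3 together with the aim of finding the most dose-sensitive measure.

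The size cannot be stated. Under the assumed f and r, the ratio's standardised effect runs from zero to 1.58 times that of ECF. The documents do not show that the ratio is the wrong choice or that a true effect would be missed across the fluid measures as a whole. They leave the comparison of bioimpedance metrics unplanned although the data will exist. It should be corrected before analysis; it does not undermine the trial.

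**What to change.** Keep the planned ECF/ICF analysis. Add to 8.2.1:

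- The same within-day, between-day and final models for log ECF and log ICF of the study leg, with log(ECF/ICF) as their difference. That identity is exact for each subject. Arm contrasts may not subtract exactly once each model has its own baseline term, so fit the log ratio as well.
- The same models for bioimpedance-derived limb fluid volume, whole leg and by segment where measured. If the sponsor intends perometry alone to serve this endpoint, amend 5.2 to say so.
- Each outcome's own baseline value as a fixed covariate, not one tested for inclusion.
- Arm contrasts for all bioimpedance metrics side by side with confidence intervals, and ECF and bioimpedance volume entered beside the ratio in the endpoint ranking.
- A statement that the ranking is exploratory.

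The cost is SAP wording and analyst time. ECF, ICF and whole-leg volume across three analyses make 3 × 3 = 9 extra runs, the log ratio adds 3 for 12, and each leg segment adds 3 more. No new measurements are needed, and the sample size is unaffected because it is not power-based. The real downside is the longer list of candidates ranked on 10 subjects per arm, which is why the intervals and the exploratory label are needed.

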5.0 Study Design

5.1 Overview of Study Design: This study is a 3 arm, prospective, randomised, proof of principle clinical trial to determine the optimal treatment duration for achieving a measurable physiologic effect on lower extremity lymphoedema with the Flexitouch® system (FT) as determined by bioimpedance, perometry, tonometry, ultrasound, local tissue water assessment, symptom burden and subject interview.. Each intervention arm will include 10 completed subjects for a total of 30 completed subjects.

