8.2.2 Analysis of Subcutaneous Tissue Density/Fibrosis

Subcutaneous tissue density and fibrosis are being assessed using one method, namely tonometry. Tonometry will be assessed at two or 3 time points depending on study group, at baseline (prior to first treatment), and after the final treatment on day 5 and day 12 if applicable. A repeated measures mixed linear model will be used to determine the changes in subcutaneous density at these time points. Randomised group will be forced into the model. Other covariates considered for inclusion in the model will include BMI, time of day measurements are taken, activity level (number of hours upright and ambulatory), age and number of hours utilizing compression garments.

8.2.3. Analysis of Patient Reported Outcomes.

Patients' self-reported symptoms and change in symptoms are recorded using the MYMOP questionnaire. Analysis will be undertaken to compare the intensity of the self-reported symptoms using a repeated measures analysis, with BMI, activity level (number of hours upright and ambulatory), age and number of hours utilizing compression garments.

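### The change-from-baseline models leave each fluid outcome's Day 1 value to an unspecified entry test; forcing it in is a cheap improvement

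*Combined protocol and SAP*

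**What the plan says.** Section 8.2.1 uses change in ECF/ICF as the dependent variable in a linear mixed model. Group and visit day are forced. Everything else, starting with "ECF/ICF ratio at baseline, BMI, time of day measurements are taken", "will be tested for inclusion in the model". No significance level or other entry rule is stated. The between-day and final analyses reuse the same candidates.

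Local tissue water is to be handled similarly. For perometry, "The analysis will therefore be undertaken in an identical way as for the bioimpedance measurements". Neither paragraph names that outcome's own Day 1 value.

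Section 8.2.2 forces group for tonometry and then says "Other covariates considered for inclusion in the model will include BMI, time of day measurements are taken"; no baseline tonometry reading is listed. However, the same section makes the reading before first treatment one of the modelled time points. Section 8.2.3 lists covariates for a repeated-measures analysis of MyMOP, again with no baseline score. The schedule in Section 7.2 codes Day 1 MyMOP as collected during the visit, not before treatment.

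On size and purpose, Section 5.1 says "Each intervention arm will include 10 completed subjects for a total of 30 completed subjects", and Section 8.2 says "This small sample size will not offer a powered statistical analysis for any single outcome measurement" and "The study will be used to find the effect size for comparisons between the doses".

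**The concern.** In a randomised comparison, the pre-treatment value of the outcome is usually among its strongest predictors, and here it is already collected. A change score uses that value but fixes its coefficient at 1. If the pre/post correlation is below 1, an arm that starts high by chance tends to show a larger fall whatever the dose. Adjusting for baseline removes this.

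Testing baseline for entry means that the adjustment happens in some trials and not in others, and for some outcomes and not others, depending on the data. With 30 subjects such a test often misses a real predictor. The contrasts affected are the effect sizes meant to plan the later study.

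**Working it through.** **The plan's own figure.** The sample size is 3 x 10 = 30. No SD, effect size, alpha or power lies behind it, and for bioimpedance "At present there is no indication of the magnitude of the effect expected using bioimpedance". There is no calculation to reproduce.

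**Inputs.** From the documents: 10 completers in each of 3 arms, a change score as dependent variable, group forced. Assumed, because the documents are silent: outcome SD = 1 before and after, pre/post correlation rho of 0.5 to 0.9 (with 0.95 and 0.98 as extremes), and two-sided 5% for both the entry test and the contrasts.

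**Chance imbalance.** The SD of the baseline difference between two arms is sqrt(2/10) = 0.447 SD. P(|difference| > 0.5) = 2 x [1 - Phi(0.5/0.447)] = 0.26. For at least one of the three pairs it is 0.50 (simulated).

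**Error given imbalance.** An unadjusted change-score contrast is shifted by (rho - 1) x imbalance. For an imbalance of 0.5 SD: -0.25 at rho 0.5, -0.15 at 0.7, -0.10 at 0.8, -0.05 at 0.9.

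**Precision of forcing, against no baseline term.** Contrast variance is proportional to 2(1 - rho) for the change score. With baseline forced it is (1 - rho²) x [1 + 1/(30 - 3 - 2)] = 1.04(1 - rho²). The ratio is 0.52(1 + rho): 0.78 at rho 0.5, 0.88 at 0.7, 0.94 at 0.8, 0.99 at 0.9, 1.01 at 0.95, 1.03 at 0.98. Break-even is rho = 2/1.04 - 1 = 0.923.

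**The plan's rule (test, then include).** 20,000 simulated trials per rho, 3 x 10 subjects, one change score each, no true dose difference:

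| rho | baseline kept | SD of contrast, tested | SD of contrast, forced | excess variance |
|---|---|---|---|---|
| 0.5 | 80% | 0.4068 | 0.3972 | 5% |
| 0.7 | 54% | 0.3321 | 0.3226 | 6% |
| 0.8 | 38% | 0.2789 | 0.2729 | 4% |
| 0.9 | 21% | 0.2005 | 0.1987 | 2% |
| 0.95 | 12% | 0.1415 | 0.1420 | about 0 |

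Excess variance is the squared ratio of the two SDs minus 1; at rho 0.7, (0.3321/0.3226)² = 1.06. At rho 0.9, repeat runs give 1 to 2%.

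**Mean contrast error where the first arm starts more than 0.5 SD higher:**

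| rho | no baseline term | tested | forced |
|---|---|---|---|
| 0.5 | -0.357 | -0.030 | 0.009 |
| 0.7 | -0.226 | -0.071 | -0.008 |
| 0.8 | -0.144 | -0.055 | 0.004 |
| 0.9 | -0.072 | -0.039 | 0.000 |

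At rho 0.7 testing leaves 0.071/0.226, about a third, of the unadjusted error. The 95% interval half-width with baseline forced is 0.669 SD there, so the residual is about a tenth of it (0.071/0.669 = 0.11).

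**Scope.** These figures describe one change from Day 1 per subject, as in the final analysis. They are only indicative for the between-day model with several visits. They do not cover within-day change from Day 2, which is post minus same-day pre: with equal correlations its covariance with the Day 1 value is rho - rho = 0, so the Day 1 value gives no such gain.

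**The case against.** The strongest reply is that the rule as written costs little. At most it adds 6% to the variance, which is about 3% on the standard error (sqrt(1.06) = 1.03), in a study that disclaims power. The test also tends to drop baseline where it matters least: at rho 0.9 it is usually dropped, but omission then costs only about 1%. This stands and sets the size of the point. It does not justify keeping the test, which no result above favours by more than simulation noise.

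Several stronger readings are tempting, and the documents do not support them:

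- A reader might infer a variance penalty of 28% (1/0.78 at rho 0.5). That belongs to a change score with no baseline term, which is not the rule for the fluid outcomes.
- A reader might call the adjustment free. It costs one degree of freedom and about 4% of variance. Above rho of about 0.92 it is slightly less precise than the plain change score. Limb volume over 5 to 12 days could lie there; the documents give no correlation.
- A reader might take the perometry sentence literally, as testing baseline ECF/ICF in a volume model. That is strained: the same reading would make ECF/ICF the dependent variable too. The natural reading substitutes limb volume throughout.
- A reader might conclude that tonometry and MyMOP ignore baseline. Day 1 tonometry is a modelled response, and Day 1 MyMOP may be. The gap there is an unstated model: no group-by-time term and no common-baseline constraint.
- A reader might say that the ranking of endpoints is distorted. No calculation here shows that.

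**Conclusion.** The point holds as a cheap improvement. In the change-from-baseline models of Section 8.2.1, baseline should be a fixed part of the model and not a candidate. Under an assumed 5% entry test and rho of 0.5 to 0.9, the current rule omits it in about 20 to 80% of trials, adds about 1 to 6% to contrast variance, and leaves an error of about -0.03 to -0.07 SD when the first arm of a pair starts more than 0.5 SD higher.

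This concerns precision and bias conditional on an observed imbalance. Averaged over randomisations the contrasts are unbiased, and nothing here invalidates the design. The 26% imbalance figure needs only 10 per arm and approximately normal means. Every other size rests on the assumed correlation, and those for the plan's rule also on the assumed threshold.

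**What to change.** - **Between-day and final models for ECF/ICF, local tissue water and limb volume.** Force that outcome's own Day 1 pre-treatment value alongside group and day, name it for each outcome, and remove it from the candidates to be tested.
- **Within-day models.** If a baseline term is used, state that it is the Day 1 pre-treatment value. From Day 2 the same-day pre-treatment value is measured after randomisation and earlier treatment.
- **Tonometry.** Choose one of two specifications: a common-baseline repeated-measures model with group-by-time terms, or Day 1 as a covariate with the Day 1 rows removed from the response. Adding the covariate without removing those rows would put the same number on both sides of the model.
- **MyMOP.** Apply the tonometry approach only if the Day 1 questionnaire is confirmed as completed before treatment.

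The cost is a few sentences in Section 8.2 and one degree of freedom per model, about 4% of variance. The net loss of precision is 1 to 3%, and only if the correlation exceeds about 0.92. No extra subjects, visits or measurements are needed.

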Group A: subjects will receive 12 consecutive days of treatment utilizing the following treatment regimen. The first 5 days will be in clinic (Monday through Friday) followed by self administered at home treatment for 2 days (Saturday and Sunday). The last 5 days of treatment will be in clinic ending the treatment phase on day 12 (Monday through Friday).

- One lower extremity treatment per day using program L1 with the pressure set to "normal" applying the full garment set.

Groups B & C subjects will receive 5 consecutive days of treatment in clinic (Monday through Friday) utilizing the following treatment regimens.

- Group B: Two lower extremity treatments per day (am and pm) using program L1 with pressure set to "normal" applying the full garment set.
- Group C: Two consecutive treatments 2 times a day (am and pm) using program L1 with pressure set to "normal" applying the full garment set.

In the case of bilateral lymphoedema, the leg with the largest volume will be considered the study leg. The contralateral (non study) leg will be treated in the same manner that it was being treated prior to entering the study. Limb volume measures for both legs will be collected.

At the screening visit, each subject's compression garment(s) will be assessed for clinical adequacy (Class: $\geq 20\text{mmHg}$; Age: 3 months or less) by the Principal Investigator. Subjects will be instructed to wear the compression garment(s) every day during wakeful time. Garments may be removed while bathing and overnight. The clinician will remove the subject's compression garment during device treatment. This treatment regimen is consistent with standard home care compression garment(s) treatment.

7.2 Subject Data Requirements: The following data will be collected from all subjects:

Key: B = Before Treatment A = After Treatment D = During Visit	Screening	Baseline/ Initial Treatment (D1)	Treatment (≠ D1, 5 & 12)	Day 5(All Groups) and Day 12 (Group A)
Medical History	D			
Bio Impedance		B A	B A	B A
Perometer		B A	B A	B A
Duplex U/S	B			
Interface Pressure		B	B	B
Ultrasound		B		A
Tonometry		BA	BA	BA
Moisture Meter D		B A*	B A*	B A*
Subject Interview				D
MyMOP		D		D
Activity Level		D	D	D
BMI		D	D	D
Adverse effects		A	A	A
Compliance		D	D	D

*Group C: Will have moisture meter done before the first treatment session, after the first treatment session, and then after the final treatment session of the day = 3 times total during treatment visits.

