7.4.8 Screening Visit: At this visit, the patient will be asked to provide written informed consent and inclusion and exclusion criteria will be evaluated to ensure that the patient meets all entrance criteria. See section 7.2 for a schedule of events.

After the informed consent process is complete, the subject will be randomised into one of 3 study groups. The baseline visit must occur on a Monday. Study staff and the subject will make every attempt to schedule all study visits at the same time of day.

At this visit, the subject will withdraw all at home lymphoedema treatments with the exceptions of wearing appropriate compression garments and maintaining proper skincare. Subjects cannot use limb bandaging at any time during the study.

The subject will leave the screening visit with:

- Schedule for all study visits with the first treatment visit starting on a Monday.
- Pedometer and instruction to start wearing the morning of the first treatment visit
- Diary to record daily activity and instructions to start documenting the morning of the first treatment visit
- Contact information and instructions to call if any problems arise

7.4.9 Baseline Visit/Initial Treatment: At the time of the baseline/initial treatment visit the subject will undergo the study procedures according to the table in section 7.2.

During the visit the subject will undergo treatment according to which group they were randomised. For Groups B and C which receive FT treatment twice a day the subject must have at least 2 hours and no more than 6 hours between the am and pm treatment sessions. The compression garment must be worn between the am and pm treatment sessions.

7.4.10 Treatment Visits (Group A: Day 2 to 5; 8 to 12; Group B & C: Day 2 to 5): The subject will be examined, receive FT

treatment according the treatment group assigned and the study parameters according to the table in section 7.2 will be completed and recorded by appropriately trained study staff.

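### Activity level and garment hours are recorded only after randomisation, yet may enter the dose-comparison models; the regimen itself changes garment hours, so adjusted contrasts can be biased, in a direction the documents do not settle

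*Combined protocol and SAP*

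**What the plan says.** **Model terms.** For bioimpedance, 8.2.1 forces in group and day of visit. Among the remaining candidates, "activity level (number of hours upright and ambulatory), age, number of hours utilizing compression garment, will be tested for inclusion in the model". No test, threshold or order is given. For the between-day model, "Identical confounding variables will be used as for the within day analysis". Perometry is to be handled identically to bioimpedance, and local tissue water similarly. For tonometry, 8.2.2 also treats activity and garment hours as candidates. For MYMOP, 8.2.3 lists them with no entry test.

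**Timing.** In 7.4.8 (screening visit), "After the informed consent process is complete, the subject will be randomised into one of 3 study groups". The subject leaves that visit with: "Pedometer and instruction to start wearing the morning of the first treatment visit"; and "Diary to record daily activity and instructions to start documenting the morning of the first treatment visit". The 7.2 schedule, introduced by "The following data will be collected from all subjects", has no screening entry for Activity Level or Compliance. At screening, 7.1 checks garment class and age, not hours worn.

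**Garment wear.** In 7.1, "Subjects will be instructed to wear the compression garment(s) every day during wakeful time", but the clinician takes off the "compression garment during device treatment". Section 7.4.9 requires Groups B and C to wear the garment between the morning and afternoon sessions, which are 2 to 6 hours apart.

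**Use of the results.** Section 8.2 intends the estimates to show which endpoints respond most to dose, to select a primary endpoint, and to size a definitive study.

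**The concern.** A covariate measured after randomisation and altered by the assigned regimen is not a confounder, although 8.2.1 uses that label. If garment hours affect the outcome, adjusting removes part of what the regimen does. If they share an unmeasured cause with the outcome, adjusting brings in a bias that randomisation had excluded. If neither holds, precision is lost. The plan itself treats both variables as results: activity is an endpoint in 5.2, and garment compliance is an adherence measure in 8.3.

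Effect estimation is this pilot's purpose, so a systematic shift in a contrast carries straight into the choice of endpoint and the size of the next trial. Data-driven entry could also leave different covariates in for different endpoints, so that their contrasts would not mean the same thing.

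**Working it through.** **1. Device hours (8.2, with the regimens in 7.1).** The stated totals reproduce at 1 h per treatment: A 12 days × 1 = 12 h; B 5 days × 2 = 10 h; C 5 days × 4 = 20 h. Per treatment day: 12/12 = 1 h, 10/5 = 2 h, 20/5 = 4 h.

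**2. Effect of the arm on garment hours (inferred from the wear and removal rules).**
- Whole day: with the garment off during sessions, C loses 4 − 1 = 3 h more than A, so the arm tends to lower garment hours in C.
- Within-day window, from the pre-treatment measure to the measure after the day's last session (8.2): A has one session and so about 0 garment hours in the window. B and C have the 2 to 6 h gap, midpoint 4 h, so the arm tends to raise garment hours in C.

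Section 8.2.1 does not say over which window garment hours are counted, so even the sign of the C-A difference is open.

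**3. Illustration.** All of these inputs are assumed; the documents give none except 10 per arm. There is one outcome per subject with residual SD 1, a direct C-A effect of 0.80, b = 0.1 SD of outcome per garment hour, and within-arm SD of garment hours 2 h.

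Contrast as randomised = 0.80 + b × (C-A difference in garment hours). If garment hours are always adjusted for, the contrast returns to 0.80.

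| C-A garment hours | As randomised | Entry at p<0.05 (simulated mean) | Always adjusted |
|---|---|---|---|
| −3 h | 0.80 − 0.30 = 0.50 | about 0.62 | 0.80 |
| +4 h | 0.80 + 0.40 = 1.20 | about 1.03 | 0.80 |

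In the first row garment hours were kept in about 17% of simulated trials. The shifts are 0.62 − 0.50 = 0.12 and 1.03 − 1.20 = −0.17. The pilot's standard error for a pairwise contrast is √(2/10) ≈ 0.45.

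**4. Range, in the −3 h setting.**
- b = 0.05: 0.65 as randomised, about 0.69 with p<0.05 entry.
- b = 0.1, garment SD 1 h or 3 h: 0.59 or 0.66 with p<0.05 entry.
- b = 0.1, garment SD 2 h, looser entry at p<0.20: about 0.72.
- Repeated measures over days 1 to 5 (random intercept, intraclass correlation 0.3 to 0.7, p<0.05 entry): shifts of 0.14 to 0.26 SD at b = 0.1 and 0.05 to 0.08 SD at b = 0.05. This version omits Group A's later visits, on days 8 to 12.

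**5. No garment effect and no shared cause.** There is no bias, only lost precision. If garment hours are always kept, the C-A variance is multiplied by about 1 + [3²/(27 × 2²)]/(2/10) = 1.42 in the −3 h setting. Simulation, which also includes chance imbalance, gives 1.49, or about 1.5-fold. With p<0.05 entry it gives 1.13-fold.

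**The case against.** The strongest reply is that the direction is not known. This stands: the rule in 7.4.9 points the opposite way from the removal rule in 7.1 for the within-day model. A reader might infer that adjustment inflates the contrast and would undersize the next trial; the documents do not support that.

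A second reply is that 3.1 gives garment testing a purpose: the study concerns device dosing, and 3.1 foresees learning from the data whether garments influence the device effect. This also stands, but it supports a secondary analysis. Section 3.1 also says garment use will not be formally evaluated, and no section defines a device-only contrast as the target. Adjustment would give that contrast only if nothing unmeasured drives both garment hours and outcome.

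Third, the plan disclaims power and the shifts are below the standard error. Both are true, but a confidence interval does not reveal a systematic shift.

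Fourth, the wording in 8.2.1 that treats perometry identically and local tissue water similarly may mean one fixed covariate set. If so, the risk of different covariates among the fluid endpoints goes. If it means only the same procedure, the risk remains.

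Three further readings go too far. A reader might infer that the arm changes activity; no such effect is shown, and the objection there is only that activity is recorded after randomisation and is itself an endpoint. A reader might infer that endpoints will be ranked wrongly; no such error is shown, and 8.2 sets an order of importance in advance. A reader might extend the missing entry rule to 8.2.3; that section has no entry test, so only the timing problem applies there.

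**Conclusion.** The point holds and should be corrected before analysis. Sections 8.2.1 to 8.2.3 admit two post-randomisation variables into the dose contrasts, and the regimen changes at least one of them, garment hours. Bias arises only if garment hours affect the outcome or share a cause with it. Its size and direction are unknown from the documents. Under the assumed inputs the main illustration gives shifts of about +0.12 or −0.17 SD, depending on whether C has 3 fewer or 4 more garment hours than A. Weaker garment effects give smaller shifts. The arm effect on garment hours is itself an inference from the wear and removal rules and the implied 1 h per treatment, not something the plan states. The documents show no loss from the way the day-1 value is handled in 8.2.2 and 8.2.3, and the point does not extend there.

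**What to change.** 1. Remove activity level and garment hours from the main models in 8.2.1 to 8.2.3, and report both by arm.
2. Use them only in a sensitivity analysis labelled as such, which states the contrast it targets and the window over which garment hours are counted. This still serves the garment question in 3.1.
3. Replace the open-ended covariate selection in 8.2.1 and 8.2.2 with one short fixed list of pre-treatment covariates, the same for every endpoint, for example age and BMI. The 7.2 schedule marks BMI only as taken during the visit, so specify a value taken before the first treatment.
4. In 8.2.1, force in the outcome's day-1 pre-treatment value. The gain is small: with p<0.05 entry instead, the variance is about 5%, 6% and 2% higher at baseline correlations of 0.5, 0.7 and 0.9 (simulated, change score, 30 subjects).

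The cost is wording in the statistical plan plus a note on when day-1 BMI is taken; the data are already collected. The downside is that the main models no longer describe activity or garment effects, which move to the sensitivity analysis.
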